	
 
• Incisional hernia repair rate within 2 and 5 years after surgery
 
• Re-operations due to mesh- or hernia within 2 and 5 years from surgery
 
• Quality of life (RAND-36, AAS, PROMIS) within 30 days, 2 and 5 years from surgery
 
• Medico-economic explorative measures 
 
◦ Time to create the retrorectal space and insert the mesh
 
◦ Length of stay
 
◦ Costs of materials used to close the abdomen
 
◦ Length of sick leave
 
 
 

	
At least 244 subjects will be enrolled in this study (122 per group, including 20% off lost to follow-up during 2 years interval).
 
All patients undergoing midline emergency laparotomy during the enrollment period will be screened for inclusion and exclusion criteria and recorded at study sites in order to identify any selection bias.

Randomization	
Patients having emergency midline laparotomy for any gastrointestinal indication and fulfilling the inclusion criteria, will be randomized prior to surgery after giving informed consent to the study.
 
Patients are randomly allocated (1:1 ratio) either to an intervention group or a control group according to a computer-generated list compiled by a biostatistician otherwise uninvolved in the clinical care of trial patients.
 
Allocation will be stratified according to BMI (<30 and <math>\geq 30\text{kg/m}^2</math>), history of previous midline laparotomy and age (<65 and <math>\geq 65</math>- years) and blocked within strata using random permuted blocks (block size 2, 4, 6 and 8). A separate randomization list will be created for each participating center.

Total Study Duration	
Approximately 7-8 years:
 
 
• Site start-up: 3 months
 
• Study Enrollment: 24 months
 
• Short term follow-up: Discharge, 30 days
 
• Long term follow-up: 2 years and 5 years
 

Inclusion/ Exclusion Criteria	
Study Inclusion:
 
 
• Midline emergency laparotomy for any gastrointestinal indication
 
 
Study Exclusion:

Number of  
Patients

- Previous ventral hernia repair with mesh in the midline
  - Previous inguinal or femoral hernia repair by any technique with mesh is accepted
- Previous WHO class of physical activity 3-4 (WHO 3 more than 50% of time at rest, WHO 4 stays at rest most of the time)
- Relaparotomy

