Data Collected	
Data collected will include the following:
 
 
Demographics, Patient Characteristics, and Pre-operative History: Age, BMI, previous surgical history, comorbid conditions and medications, history of smoking, previous hernias and hernia related operations
 
Intra-Operative Assessment: Prophylactic antibiotics, ASA, presence of hernias in midline, rectus diastasis, operative time, blood loss, contamination class, surgical procedure, ostomy creation and its' location from midline, length of wound, length and type of suture materials used, drains, vacuum assisted closure, other temporary closure method used, skin closure.
 
Post-Operative Assessment through Discharge: Surgical site infections, complications, re-operations, pain score (VAS) at discharge, Quality of life questionnaire, seromas, burst abdomen, fascial dehiscence, length of stay, mesh removals, length of planned sick leave, place of discharge.
 
Follow-Up Assessments: complications, clinically and/or radiologically detected hernia rate, procedure- or incisional hernia-related readmissions, procedure- or incisional hernia-related reoperations, QoL (RAND-36, AAS, PROMIS) and economic measures, pain of abdominal wall, long-term seromas.
 
 
Data will be collected 2 and 5 years postoperatively.

Data collection	Primary data collection will be performed by participating surgeons using electronical database.
Statistical Analysis	All analyses will be performed by or under the guidance of professional statistician and following the CONSORT guidelines. The primary endpoint as well as other categorical data will analysed by $\chi^2$ -test or Fisher's exact test. Ninety-five % confidence intervals (95% CI) are presented for between group differences (effect sizes). The incidence of hernia will also be analyzed using Kaplan-Meier analysis. Student's t-test or

	
Welch test will be used for continuous variable, the latter if assumption of homogenous variances does not hold.
 
Linear mixed model (LMM) or generalized linear mixed model (GLMM) will be used for repeatedly measured data, the previous for continuous data and latter for categorical data.

Finance	
Materials and visits are funded by hospital districts as part of treatment expenses. External funding will be applied to cover the costs caused by imaging.

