#### 2.2. Incisional hernia etiology

The etiology of incisional hernia is multimodal. The site and orientation of the incision has an influence on the IH rates. Non-midline incisions—both paramedian and transverse—carry a significantly reduced risk of IHs compared to midline incisions (10-11) . Suturing technique and the suture material used affect the hernia rate as well. Taking small bites of 5 mm with an intersuturing space of 5 mm with slowly absorbable monofilament suture results in a lower hernia incidence compared to large bite mass suturing (4-5, 12-14) .

There is lack of evidence of basic biological pathogenesis of incisional hernias (IH). Specific features of connective tissue and the quality of fibroblasts are proposed to have an influence on the risk for hernia formation (15). The inflammatory response after an incision results in the fibroproliferative phase. Incisional hernia may be a result of disturbance in the fibroblast proliferation in the laparotomy wound matrix (16).

Fascial ischemia is presumed to be one crucial factor in the development of an IH. The fascia is hypovascular and a wound experiences hypoxic stress immediately after surgical incision, which has been considered a major risk factor for wound failure. Hypoxia interferes with angiogenesis and the healing process (17). The revascularization at the wound site is critical to improve healing response (18). Good surgical skills and maintaining sufficient perfusion in the wound area are important issues to be noted (19).

Along with previously mentioned physiological alterations, patients' comorbidities and characteristics can predispose them to develop of a hernia (9) . Connective tissue disorders increase the risk for herniation among various other patient-related factors (20, 21). One of the most common risk factor, that increase the likelihood of development an IH is smoking (75 %) (22). As a result of an analysis of 14,618 patients, Bosanquet in his review and meta-regression determined the factors affecting midline IH rates: diabetes mellitus, obesity, cachexia, increasing age, male sex, chronic obstructive pulmonary disease (COPD), a history of or operation for an abdominal aortic aneurysm (AAA), anaemia, smoking, corticosteroids and surgical site infection (SSI). Summarising the results of 56 publications, the prevalence of IHs after midline laparotomy was 12.8 % (range: 0 to 35.6 %) with a mean follow-up time 23.7 months (21) .

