### 7.1. Inclusion Criteria

- Midline emergency laparotomy for any gastrointestinal indication
  - **Conversion from laparoscopy to laparotomy is considered as inclusion criteria from Study protocol version 3.0 onwards.**

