### 19.2 Allocation

Patients having emergency midline laparotomy for any indication and fulfilling the inclusion criteria will be randomized prior to surgery after informed consent is signed. Patients are randomly

allocated (1:1 ratio) either to an intervention group or a control group according to a computer-

generated list compiled by a biostatistician otherwise uninvolved in the clinical care of trial patients. Allocation will be stratified according to BMI ( $<30$  and  $\geq 30\text{kg/m}^2$ ), history of previous

laparotomy and age ( $<65$  and  $\geq 65$ - years) and-blocked within strata using random permuted blocks (block size 2, 4, 6 and 8). A separate randomization list will be created for each participating

center. All patients who have an emergency midline laparotomy during randomization period are assessed for eligibility.

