### 19.3 Endpoint analysis

All analyses will be performed primarily according to modified intention to treat (ITT) principle.

Patients who fulfill exclusion criteria intraoperatively (after randomization) will not be included in the analyses. Per protocol analyses will be used as safeguard against the risk of falsely claiming

PREEMER TRIAL 30

equality/superiority. The primary endpoint will be the incidence difference of IHs with 95% confidence interval between the study groups during 2-years follow up. Secondary outcomes are

listed previously. The primary endpoint as well as other categorical data will be analyzed by the  $\chi^2$ - test or Fisher's exact test. Student's t-test or Welch test will be used for continuous variable, the

latter if assumption of homogenous variances does not hold. The incidence of hernia will also be

analyzed using Kaplan-Meier analysis.

The linear mixed model (LMM) or generalized linear mixed model (GLMM) will be used for repeatedly measured data, the previous for continuous data and latter for categorical data. Multiple imputations of missing outcome data will be used for sensitivity analyses.

Prospectively

planned subgroup analyses are as follows: BMI>30, previous hernia and contamination class 4.

However, sample size calculation is done only for the primary end point and subgroup analyses are hypothesis generating only. The statistical programs SPSS (IBM Corp.

Released 2016. IBM SPSS

Statistics for Windows, Version 24.0. Armonk, NY: IBM Corp) and SAS (version 9.4, SAS Institute Inc., Cary, NC, USA) will be used for the analyses.

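### Allocation is stratified by BMI, previous laparotomy and age, but the primary test ignores the strata; a stratified test is a small, cheap gain. Separately, the laparotomy factor is worded in two ways

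*Protocol*

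**What the plan says.** **Allocation.** Protocol section 19.2 states: "Allocation will be stratified according to BMI" (below 30, or 30 and above). Previous laparotomy and age (below 65, or 65 and above) are the other two factors. Permuted blocks of 2, 4, 6 and 8 are used within strata. The synopsis (section 1) adds "A separate randomization list will be created for each participating center", and section 19.2 repeats this, so centre is in effect a fourth factor.

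**Primary analysis.** Section 19.3 fixes the effect measure: "The primary endpoint will be the incidence difference of IHs with 95"% confidence limits, over two years. It then fixes the test: "The primary endpoint as well as other categorical data will be analyzed by the" chi-square or Fisher's exact test. The synopsis says the same ("The primary endpoint as well as other categorical data will analysed by" either test). Section 19.3 adds Kaplan-Meier, per-protocol and multiple-imputation analyses, plus mixed models for repeated measures. None of these is said to use the stratification factors. BMI above 30 appears only as a subgroup.

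**Prognostic factors.** Section 2.2 lists determinants of midline hernia, among them "diabetes mellitus, obesity, cachexia, increasing age, male sex". Two of the three stratification factors, obesity and age, are in the list; previous laparotomy is not.

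**Laparotomy factor.** The synopsis has "history of previous midline laparotomy and age". Section 19.2 describes the same factor without the word midline.

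**The concern.** Stratified allocation balances the arms on the chosen factors. If those factors predict hernia, the true variance of the between-arm difference is smaller than the unstratified formula assumes. The unstratified test is then mildly conservative, and its interval slightly wider than it needs to be. The protocol's own background names two of the factors as prognostic, so it is natural to ask why the analysis does not use them. What is at stake is a little precision. The trial's validity is not in question.

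The two wordings of the laparotomy factor are a different kind of problem: a contradiction within current text. Under the synopsis, a patient whose only earlier laparotomy was non-midline has no such history; under section 19.2 the patient has one. This does not affect the planned unstratified test. It does leave unclear which stratum such a patient was randomised in, and with a separate list at each centre, sites could classify the same patient differently. Any stratified analysis, or any report by stratum, needs this settled.

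**Working it through.** **1. The protocol's own figure.** Inputs from section 19.1: 25% v 10%, alpha 0.05, power 80%, dropout 20%. Sidedness is not stated; two-sided reproduces the result. With unpooled variance:

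n = (1.960 + 0.842)² × (0.25×0.75 + 0.10×0.90) / 0.15² = 7.849 × 0.2775 / 0.0225 = 96.8, so 97 per group.

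97 / 0.8 = 121.25, so 122 per group and 244 in total. Both stated figures reproduce. Exact enumeration at 97 per group gives 80.2% power for the uncorrected chi-square test and 74.6% for the two-sided Fisher test.

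**2. Simulation of the stratified alternative.** The protocol gives neither factor prevalences nor odds ratios, so these are assumptions:
- prevalences 30% (BMI), 30% (laparotomy) and 50% (age);
- five sets of odds ratios, from none prognostic to strong;
- 1, 5 or 10 centres, with no centre effect;
- 20% lost at random from 244 (about 195 analysed).

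Allocation followed section 19.2. Risks were calibrated to marginal rates of 25% v 10% for power and 25% v 25% for the null. There were 10,000 trials per setting; the Monte Carlo standard error is about 0.4 points for power, 0.2 for null rejection and coverage, and 0.14 to 0.25 for the paired difference in power.

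| Odds ratios (BMI / laparotomy / age) | Power, CMH over 8 strata minus chi-square (points) |
|---|---|
| 1 / 1 / 1 | -0.9 to -0.4 |
| 2 / 1 / 1.5 | -0.6 to +0.2 |
| 2 / 1.5 / 1.5 | -0.3 to +0.3 |
| 3 / 1 / 2 | +0.7 to +1.2 |
| 3 / 2 / 2 | +0.9 to +1.8 |

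Across all settings:
- power: chi-square 79.9-81.5%, CMH 79.4-82.6%;
- null rejection: chi-square 4.4-5.2%, CMH 4.8-5.3%;
- 95% interval coverage: crude difference 94.5-95.5%, Mantel-Haenszel difference (Sato variance) 94.4-95.0%;
- mean interval width: crude 20.8 points; Mantel-Haenszel 0.1-0.2 wider at 1/1/1 and 0.5-0.6 narrower at 3/2/2.

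**3. Independent simulation.** This used 97 per group, 4 centres, 6,000 trials per setting and the same odds ratio for every factor:

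| Odds ratio per factor | Power, chi-square v CMH | Null rejection, chi-square v CMH |
|---|---|---|
| 1 | 80.8% v 80.3% | 5.0% v 5.1% |
| 1.5 | 79.8% v 79.5% | 5.4% v 5.4% |
| 2 | 81.2% v 81.6% | 4.7% v 4.9% |
| 3 | 80.8% v 83.5% | 4.0% v 5.0% |

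The pattern is the same: no gain when the factors are weak, up to 2.7 points when all three are strong.

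**4. Centre.** Crossing the eight strata with centre leaves cells with patients in one arm only, and these drop out of CMH. With 5 centres, 5% of patients are lost this way and power is 75.3-77.8%. With 10 centres, 16% are lost and power is 68.6-70.6%.

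**5. Model-based alternative.** A standardised risk difference from logistic regression with the plain influence-function standard error rejects a true null in 5.3-5.9% of trials without centre, 5.5-6.1% with 5 centres and 6.3-6.6% with 10 centres as main effects. With a leverage-corrected standard error and no centre, the figure is 4.5-5.1% and power is within 0.6 points of CMH. It has no advantage over CMH here.

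**6. Laparotomy wording.** The protocol does not say how many patients have only a non-midline scar. If 5-15% do (assumption), 244 × 0.05 = 12 to 244 × 0.15 = 37 patients would be classed differently under the two wordings.

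**The case against.** The strongest reply is that an unadjusted chi-square test with a risk difference is a coherent, valid pairing, and that adjustment is commonly left to the statistical analysis plan, which is not at hand. It would add that three of the five scenarios show a loss or no clear gain, that the odds ratios are assumed, and that the proposed test still leaves out centre. Changing a valid primary test mid-trial may also invite suspicion of a post-hoc choice. Section 7.1 shows the protocol has been revised during the study ("Conversion from laparoscopy to laparotomy is considered as inclusion criteria from Study protocol version 3.0 onwards"), and section 9.1 plans between-group complication analyses. On the wording, each patient was randomised under one definition, so nobody actually moved stratum.

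Much of this stands. The planned test is valid, the gain may be nil, and an adjusted sensitivity analysis would give much of the same information. The simulations also do not model the intra-operative exclusions, which would thin the strata further. But the protocol itself names the primary test, so that choice can be reviewed here. The possible loss is under one point of power. Centre is left out deliberately, because crossing it with the strata costs far more than it could return. The timing objection limits who may write the amendment and when; it does not rule the amendment out. And although no patient moved stratum, a reader of the protocol cannot tell which definition was applied.

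**Conclusion.** Both parts hold, and both are small. The primary test does not use the stratification factors. CMH would change power by about -0.9 to +1.8 points under the main assumptions, and by up to +2.7 if all three factors had an odds ratio of 3. The interval would be between 0.2 points wider and 0.6 points narrower. The unadjusted test does not inflate the error rate; with strong factors it is slightly conservative. The sample size need not change. These figures rest on the assumed prevalences and odds ratios, no centre effect and loss at random.

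The laparotomy wording is a plain contradiction and needs no assumption to establish. Only the count of 12 to 37 patients is assumed. It should be corrected whichever test is kept.

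**What to change.** In section 19.3 and the synopsis, name one primary analysis: a CMH test without continuity correction over the eight BMI × laparotomy × age strata as recorded at randomisation, with a Mantel-Haenszel risk difference and 95% confidence interval. Do not cross the strata with centre. Keep the chi-square test and crude difference as a sensitivity analysis. If a standardised logistic risk difference is preferred, use a small-sample-corrected standard error and no centre main effects. Naming one test also settles the open choice between chi-square and Fisher.

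Separately, word the laparotomy factor identically in the synopsis and section 19.2, using the definition programmed in the randomisation list.

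The cost is a short amendment and no new data, since the factors are known at randomisation. It must be dated and written by people who have not seen outcomes by arm. If no factor turns out to be prognostic, the price is 0.4 to 0.9 points of power and an interval up to 0.2 points wider.

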## 6.2 Secondary Endpoints

Secondary Endpoints:

- Comprehensive Complication Index within 30 days from surgery
- Surgical site infection (SSI) rate defined by CDC classification of surgical site infection  
within 30 days follow up
- Fascial rupture within 30 days from surgery
- Incidence of Incisional hernia within 5 years follow-up
- Incisional hernia repair rate within 2 and 5 years after surgery
- Re-operations due to mesh- or hernia within 2 and 5 years from surgery
- Quality of life (RAND-36, AAS, PROMIS) within 30 days, 2 and 5 years from surgery
- Medico-economic explorative measures
  - Time to create the retrorectal space and insert the mesh
  - Length of stay
  - Costs of materials used to close the abdomen
  - Length of sick leave

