### 10.3. Study Plan

[figure not shown]
*Figure 1 Flow Chart*

Intend to treat population  
reaching 30 days control

Intent to treat  
population  
reaching 2 years  
control

Intent to treat  
population  
reaching 5 years  
control

Data will be collected at baseline, operative procedure, discharge, 30 days, 2 years and 5 years. Specific databases (Hoitoilmoitusrekisteri HILMO, Tilastokeskus) may be used to collect data of patients' survival and operations done to patient outside study sites. If there is any suspicion of

PREEMER TRIAL 17

incisional hernia raised at any point of the follow-up, the patient is advised to contact the study site and additional clinical evaluation and ultrasonography if needed is arranged. The data will be collected using electronical CRFs and software designed for this study.

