### 13. Subject Withdrawal and Discontinuation

The subject's participation in any clinical trial is voluntary. The subject and/or the representative of subject has the right to withdraw at any time without penalty or loss of benefit. Study

withdrawal means the subject is no longer participating in the study and no further study-related follow-ups will be performed. All subjects that withdraw after informed consent is signed will be evaluated at the time of withdrawal. Every effort will be made to document the subject outcome at the time of withdrawal. Data collected until withdrawal will be analyzed. The investigator has the right to discontinue subjects from the study at his/her discretion to ensure wellbeing of the subject. The reasons for withdrawal shall be documented (electronic Patient Withdrawal Request Form).

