## 19. Sample Size and Statistical Analysis

### 19.1 Sample size

To calculate a sample size needed to compare these two groups we estimated a 10 % rate of IH in mesh group and 25 % IH in control group on clinical assessment and ultrasound examination.

Assuming  $\alpha = 0.05$  and power = 80%, we would need 97 patients per group. Further, assuming a 2- year dropout rate of 20%, 122 patients per group are needed (totally 244 patients). The sample

size is calculated only for the primary outcome, the secondary outcomes will be interpreted as

hypothesis generating only. If the estimated 20% dropout rate exceeds, the sample size may be recalculated.

All analyses will be performed by or under the guidance of professional statistician and following the CONSORT guidelines.

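### Hernia repair and re-operation at 2 and 5 years are assigned to chi-square/Fisher tests, which have no place for patients followed only part of the way

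*Protocol*

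**What the plan says.** Section 6.2 of the protocol lists two secondary endpoints about later surgery: "Incisional hernia repair rate within 2 and 5 years after surgery" and "Re-operations due to mesh- or hernia within 2 and 5 years from surgery".

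Section 19.3 fixes the methods. "The primary endpoint as well as other categorical data will be analyzed by the" chi-square or Fisher's exact test. For one outcome it adds a time-to-event analysis: "The incidence of hernia will also be" analysed by Kaplan-Meier. Mixed models are kept for repeatedly measured data. On missing data it says: "Multiple imputations of missing outcome data will be used for sensitivity analyses".

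Three other places bear on the point:
- Section 13, on patients who withdraw: "Data collected until withdrawal will be analyzed".
- Section 10.3 (Study Plan): national registries "may be used to collect data of patients' survival and operations done to patient outside study sites". The flow-chart labels in the same section describe the populations at 2 and 5 years as the intention-to-treat patients who reach that control.
- Section 19.1: a 2-"year dropout rate of 20%, 122 patients per group are needed (totally 244 patients"). It gives no loss figure for 5 years. It also says that secondary outcomes are only hypothesis generating.

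**The concern.** A repair or re-operation happens on a definite day, and patients are observed for different lengths of time. A chi-square or Fisher test needs a yes or no from every patient at 2 years and again at 5 years. A patient who leaves at year 3 without an operation has no such answer at 5 years. A patient repaired at year 1 who leaves at year 3 has a known event but did not reach the 5-year control.

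The method is also placed oddly. Hernia itself is looked for mainly at the scheduled 2-year examination and ultrasound, so its onset is poorly dated, yet it gets the time-to-event analysis. The two outcomes with a natural event date do not.

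These endpoints show whether the mesh spares patients further surgery or leads to it, and section 20.1 commits to publishing 5-year results. The estimated difference should not depend on an unstated choice about how part-followed patients enter the table.

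**Working it through.** **The plan's own figure.** With 25% versus 10%, two-sided α = 0.05, 80% power and unpooled variance:

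n = (0.25×0.75 + 0.10×0.90) × (1.960 + 0.842)² / 0.15² = 96.8, so 97 per group; 97/0.80 = 121.25, so 122.

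This reproduces section 19.1. It covers the primary endpoint only and does not bear on this point.

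**Inputs for the check.** The protocol gives no repair rate, re-operation rate or 5-year loss, so these are assumptions:
- True 5-year repair 12% (control) and 5% (mesh), a difference of 7.0 points.
- Constant hazards, loss independent of repair, no deaths.
- 5-year loss of 42.8%, which is the 20% at 2 years continued at the same rate (1 − 0.8^2.5). The lower case is 30%.

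**Formulas.** Repair hazard h = −ln(1 − risk)/5 and loss hazard l = −ln(1 − loss)/5.
- Observed repairs: e = h/(h + l) × (1 − exp(−5(h + l))).
- Followed to 5 years without repair: f = exp(−5(h + l)).
- Coding A, lost patients counted as no repair: rate = e.
- Coding B, known repairs kept and unrepaired lost patients dropped: rate = e/(e + f).
- Coding C, only patients reaching 5 years: rate = true risk when loss is independent.

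**At 42.8% loss** (l = 0.1116):
- Control: h = 0.0256, e = 0.1864 × 0.4963 = 0.0925, f = 0.5037, B = 0.0925/0.5963 = 0.155.
- Mesh: h = 0.0103, e = 0.0842 × 0.4562 = 0.0384, f = 0.5438, B = 0.0384/0.5822 = 0.066.

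**At 30% loss** (l = 0.0713):
- Control: e = 0.2638 × 0.3840 = 0.1013, f = 0.6160, B = 0.141.
- Mesh: e = 0.1257 × 0.3350 = 0.0421, f = 0.6650, B = 0.060.

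| Handling | 30% loss | 43% loss |
|---|---|---|
| True difference | 7.0 | 7.0 |
| A: lost = no repair | 10.1 − 4.2 = 5.9 | 9.3 − 3.8 = 5.4 |
| B: drop unrepaired lost | 14.1 − 6.0 = 8.2 | 15.5 − 6.6 = 8.9 |
| C: completers only | 7.0 | 7.0 |

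Differences are in percentage points, taken before rounding the rates.

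**What coding C costs.** With 122 per arm, the expected number of known repairs at 43% loss is 122 × (0.0925 + 0.0384) = 16.0. Completers keep 122 × 0.572 × (0.12 + 0.05) = 11.9, so about 4 known repairs are discarded. At 30% loss the figures are 17.5 and 14.5, so about 3 are discarded.

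A simulation of 5000 trials with 122 per arm, assumed risks of 15% versus 5% and 40% loss in each arm shows the loss of precision. The standard deviation of the difference was 4.8 points for completers and 4.3 for Kaplan-Meier, and power was 54% against 66%. At 20% loss, power was 67% against 72%. No deaths were simulated, so Kaplan-Meier and a cumulative-incidence estimate coincide there.

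**Unequal loss.** With the same 15% versus 5% (true difference 10.0 points):
- Loss of 40% in control and 20% in mesh gives 7.3 points under A and 13.3 under B.
- Loss the other way round gives 9.6 and 10.1, so the shift depends on the pattern.

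With equal true risks of 10% and loss of 40% in control and 20% in mesh, A gives 7.9 − 9.0 = −1.1 points and B gives 12.7 − 11.1 = +1.6 points. Both are false differences.

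**The case against.** The case on the other side is substantial.

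- **Section 19.3 does not name these endpoints in the chi-square sentence, and it offers a generalised linear mixed model for repeated categorical data.** True, but that model is for repeated measurements. A first repair by 2 or by 5 years is a cumulative event, and a mixed model would still need a yes or no at each time. The plain reading is that these endpoints are categorical data under chi-square or Fisher.
- **Multiple imputation offers another route for patients with missing status.** It does, but only as a sensitivity analysis.
- **Registries could capture operations after a patient stops attending, and only Finnish hospitals are considered.** This could greatly reduce the loss that matters here, and the 20% dropout was set for an endpoint that needs examination and imaging. But the protocol makes registry use optional.
- **Denominator rules are commonly left to a statistical analysis plan, which is not at hand.** Agreed, and the lack of such a rule is not the point. The protocol itself assigns the method and reserves the time-to-event analysis for another outcome.
- **The relative effect barely moves.** In the 43% case the risk ratio is 12/5 = 2.4 in truth, 9.3/3.8 = 2.4 under A and 15.5/6.6 = 2.3 under B. This stands for equal, independent loss. The section 19 summary measure is the difference, and that does move.

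A reader might infer that rates and differences are distorted as soon as any patient is lost. The documents do not support that. The protocol prescribes neither biased coding. The flow-chart labels point towards a completers analysis, which is unbiased under independent loss. Nor do they support 43% as a forecast of 5-year loss; it is an extrapolation.

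**Conclusion.** The point holds in a limited form. Chi-square or Fisher is the assigned method for hernia repair and for mesh- or hernia-related re-operation at 2 and 5 years, and it has no place for partial follow-up.

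The consequence depends on the handling. A completers table loses known operations (about 3 to 4 of 16 to 17.5 in the example) and precision, and sits badly with the section 13 commitment to analyse data up to withdrawal. The other two codings can bias the difference in opposite directions: 5.9 to 5.4 or 8.2 to 8.9 points against a true 7.0. Loss that differs between arms can make this worse.

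These sizes rest on assumed repair risks, assumed loss, constant hazards and loss unrelated to repair. Optional registry capture and sensitivity-only imputation soften the problem without closing it. The primary endpoint is not affected, and the secondary outcomes are hypothesis generating, so this is a recommended improvement and not a threat to the trial's main conclusion.

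**What to change.** In section 19.3, state that hernia repair and mesh- or hernia-related re-operation will each be analysed by:
- cumulative incidence per arm (Aalen-Johansen), with death as a competing event and censoring at last known follow-up;
- the between-arm difference at 2 and at 5 years with its 95% CI; Gray's test is optional.

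Plain Kaplan-Meier would treat deaths as censored, so it is not a full remedy. Keep chi-square or Fisher for the categorical 30-day outcomes (surgical site infection and fascial rupture).

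Record the dates of operation, death and last contact on the eCRF. The collection lists in section 10.2 mention re-operations without a date, so these fields should be named. Use the registry sources already named in section 10.3 (Study Plan) where available.

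The cost is one or two sentences, slightly more analysis work and explicit date fields; no extra patients or visits are needed. The method still assumes that loss is unrelated to the outcome, so the planned imputation sensitivity analysis remains useful. The change should be made before outcome data are seen.
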